14.4. Audits and Inspections

The investigator understands that regulatory authorities, the IRB/IEC, and/or Xeris Pharmaceuticals or their designees have the right to access all eCRFs, source documents, and other study documentation for on-site audit or inspection and will retain this right from the start of the study to at least 2 years after the last approval of a marketing application or for at least 2 years after clinical development of the study drug for the indication being studied has been discontinued. The investigator is required to guarantee access to these documents and to cooperate with and support such audits and inspections.

15. QUALITY CONTROL AND QUALITY ASSURANCE

During study conduct, Xeris Pharmaceuticals or its agent will conduct periodic visits to ensure that the protocol and Good Clinical Practices are being followed. The monitor may review source documents to confirm that the data recorded on eCRFs is accurate. The investigator and institution will allow Xeris Pharmaceuticals' monitor or its designee, and appropriate regulatory authorities, direct access to source documents to perform this verification.

The study site may be subjected to review by the Institutional Review Board and/or to quality assurance audits performed by Xeris Pharmaceuticals or its designee, and/or to inspection by appropriate regulatory authorities. It is important that the investigator and study staff are available during the monitoring visits and possible audits or inspections and that sufficient time is devoted to the process.

16. ETHICAL CONSIDERATIONS

16.1. Conduct

The investigator will ensure that the study described in this protocol is conducted in full conformance with those principles, the protocol, current FDA regulations, ICH Good Clinical Practices (GCP) guidelines, GLP guidelines, local ethical and regulatory requirements, including the Federal Food, Drug and Cosmetic Act, US applicable Code of Federal Regulations (Title 21), any IRB/IEC requirements relative to clinical studies.

Should a conflict arise, the investigator will follow whichever law or guideline affords the greater protection to the individual subject. The investigator will also ensure thorough familiarity with the appropriate administration and potential risks of administration of the study drug, as described in this protocol and the Investigator's Brochure, prior to the initiation of the study.

16.2. Institutional Review Board and Ethics Committee

The IRB/IEC must be a properly constituted board or committee operating in accordance with 21 CFR Part 56, "Institutional Review Boards." This protocol, any protocol amendments, the associated informed consent forms, and the informed consent procedures must be submitted to the IRB for review and approved before the enrollment of any subject into the trial. Study drug may not be shipped to the investigator until Xeris Pharmaceuticals has received a copy of the letter or certificate of approval from the IRB/IEC for the protocol and any protocol amendments.

All types of subject recruitment or advertising information must be submitted to Xeris Pharmaceuticals or its designee and to the IRB/IEC for review and approval prior to implementation. IRB approval of any protocol amendments must be received before any of the changes outlined in the amendments are put into effect, except when the amendment has been enacted to eliminate a potential hazard to study subjects. In such cases, the chair of the IRB/IEC should be notified immediately, and the amendment forwarded to the IRB/IEC for review and approval.

It is the responsibility of the investigator to have prospective approval of the study protocol, protocol amendments, informed consent documents, and other relevant documents, eg, recruitment advertisements from the IRB/IEC. All correspondence with the IRB/IEC should be retained in the investigator file. Copies of IRB/IEC approvals should be forwarded to Xeris Pharmaceuticals.

16.3. Subject Information and Consent

All parties will ensure protection of subject personal data and will not include subject names on any sponsor forms, reports, publications, or in any other disclosures. Subject names, address, date of birth and other identifiable data will be replaced by a numerical code consisting of a numbering system provided by Xeris Pharmaceuticals to de-identify the study subject. In the case of data transfer, Xeris Pharmaceuticals will maintain confidentiality and protection of subject personal data.

The informed consent document used in this study, and any changes made during the study, must be prospectively approved by both the IRB/IEC and Xeris Pharmaceuticals before use. The investigator must ensure that each study subject is fully informed about the nature and objectives of the study and possible risks associated with participation. The investigator, or a study staff designated by the investigator, will obtain written informed consent from each subject before any study-specific activity is performed. The investigator will retain the original of each subject's signed consent document. Receipt of written informed consent will be documented in each subject's or potential subject's eCRF. The signed informed consent document must remain on file at the study site and be available for verification by the study monitors at all times.

16.4. Subject Recruitment

All types of subject recruitment or advertising information must be submitted to Xeris Pharmaceuticals or its designee and to the IRB/IEC for review and approval prior to implementation. Advertisements approved by the IRB/IEC may be used as recruitment procedures.

16.5. Reporting of Safety Issues and Serious Breaches of the Protocol

In the event of any prohibition or restriction imposed (ie, clinical hold), or if the investigator is aware of any new information which might influence the evaluation of the benefits and risks of the investigational product, Xeris Pharmaceuticals should be notified immediately. In addition, the investigator will inform Xeris Pharmaceuticals immediately of any urgent safety measures taken by the investigator to protect study subjects against any immediate hazard, and of any serious breaches of this protocol.

During study conduct, Xeris Pharmaceuticals or its agent will conduct periodic visits to ensure that the protocol and GCPs are being followed. The monitor may review source documents to confirm that the data recorded on eCRFs is accurate. The investigator and institution will allow Xeris Pharmaceuticals' monitor or its designee, and appropriate regulatory authorities, direct access to source documents to perform this verification.

The study site may be subjected to review by the Institutional Review Board and/or to quality assurance audits performed by Xeris Pharmaceuticals or its designee, and/or to inspection by appropriate regulatory authorities. It is important that the investigator and study staff are available during the monitoring visits and possible audits or inspections and that sufficient time is devoted to the process.

17. PROCEDURES FOR MODIFYING THE PROTOCOL OR TERMINATING THE STUDY

17.1. Protocol Modifications and Deviations

The principal investigator must sign this protocol and its amendments (if any) before initiating the study at a particular site. The investigator will make all reasonable efforts to comply with the written protocol. Protocol modifications to ongoing studies that affect the safety of subjects or that alter the scope of the investigation, the scientific quality of the study, the experimental design, dosing, study assessments, the number of subjects exposed to test drug, or subject selection criteria must be made only after consultation between Xeris and the investigator. All protocol modifications must be reviewed and approved by the IRB/IEC before the revised protocol can be implemented. Emergency revisions that eliminate an apparent hazard to subjects do not require preapproval by the IRB/IEC. However, the IRB/IEC must be notified in writing as soon as possible after the modification has been made. A copy of this communication must be forwarded to Xeris. All departures from the protocol must be fully documented in the source documents and the eCRFs of the subjects involved. Protocol deviations will be tracked in an electronic system implemented by the sponsor or designated representative.

17.2. Study Termination

The study may be prematurely terminated at any time because of a regulatory authority decision, change in opinion of the IRB/Ethics Committee, safety problems resulting in subject deaths, or at the discretion of Xeris Pharmaceuticals or the principal Investigator.

Circumstances that may warrant premature study termination include, but are not limited, to the following:

- Determination of unexpected, significant, or unacceptable risk to subjects,
- Failure to enter subjects at an acceptable rate,
- Insufficient adherence to the requirements of the protocol,
- Insufficient provision of complete and evaluable data, or
- Plans to modify, suspend, or discontinue development of the study drug.

If the study is prematurely terminated or discontinued, Xeris Pharmaceuticals will promptly notify the Investigators and document the reason for study termination. Specific procedures for termination will be arranged by the Sponsor in coordination with the Investigators. After notification, the Investigators must contact all participating subjects within 7 days. All study materials must be collected and all CRFs completed to the greatest extent possible, and all study materials must be returned to Xeris Pharmaceuticals or its designee within an additional 28 days.

19. APPENDICES

Appendix 1. DRAIZE SCALE

Study Personnel Instructions: The modified Draize Scale as shown in the table below will be used for physical examination/rating of abnormalities at the injection site.

The injection site should be examined for formation of both erythema and edema and results recorded in the eCRF. Evaluations of the injection site should be performed at 30, 90, and 360 minutes (\pm 2 minutes) post-treatment.

If any scores remain > 1 at the 360-minute evaluation, the subject may leave the clinic but will be instructed to contact study staff if the condition fails to resolve.

Erythema Formation		Edema Formation	
Description	Score	Description	Score
No erythema	0	No edema	0
Very slight erythema Barely perceptible	1	Very slight edema Barely perceptible	1
Well defined erythema	2	Slight edema (edges of area well defined by definite raising)	2
Moderate erythema	3	Moderate edema Raised approx. 1 mm	3
Severe erythema Beet redness to slight eschar formation	4	Severe edema Raised more than 1 mm and beyond exposure area	4

Sources:

Guidance for Industry, Skin Irritation and Sensitization Testing of Generic Transdermal Drug Products. US Department of Health and Human Services Food and Drug Administration Center for Drug Evaluation and Research (CDER). December 1999. Appendix A.

Appendix 2. INJECTION SITE DISCOMFORT ASSESSMENT

[figure not shown]
Numeric Rating Scale (NRS) for Injection Site Discomfort

Investigative Site Instructions: The subject should complete the 11-point NRS for Injection Site Discomfort at 10 and 30 minutes (\pm 2 minutes) after injection of study drug. The subject will complete the NRS by drawing a circle around the number corresponding to the perceived intensity (severity) of discomfort according to the instructions below. The goal is for the subject to report the amount of discomfort, if any, remaining at each time point, as opposed to reporting the transient pain associated with needle insertion.

Note: If a subject is unable to physically complete the questionnaire, the subject will indicate the number on the NRS corresponding to their level of discomfort, and study staff will circle it. Documentation will be provided on each completed questionnaire as to who completed the form.

Subject Instructions: Ignoring any pain from insertion of the needle, please draw a circle around the number on the scale below that corresponds to the intensity (severity) of any discomfort you are feeling **right now** at the study drug injection site.

For example, if you are currently feeling no discomfort, you should circle the number “0” on the left end of scale. If you are currently feeling the worst discomfort possible, you should circle number “10” on the right end of the scale.

Injection Site Discomfort Description and Duration Questionnaire

Study Personnel Instructions: Question 1a should be completed by the subject at **10 ± 2** minutes after injection of study drug. If response is anything other than “None,” the subject should also answer Question 1b. All subjects should also answer Question 1c at 30 ± 2 minutes post-injection.

The goal is for the subject to report the qualitative nature and duration of discomfort, if any, associated with injection of study drug, ignoring any transient pain associated with needle insertion.

Note: If a subject is unable to physically complete the questionnaire, the subject will provide verbal responses, which will be recorded on the questionnaire by study staff. Documentation will be provided on each completed questionnaire as to who completed the form.

Subject Instructions: Please answer question 1a and 1c, and, if applicable to you, question 1b. In answering these questions, you should ignore any pain from insertion of the needle.

1a. How would you describe any discomfort you felt from the study drug? (Check all that apply):

- None (Please ignore question 1b.)
- Pain (eg, throbbing, soreness, muscle ache)
- Itching
- Tingling, twitching, or numbness
- Irritation (eg, burning, stinging)

Other or additional comments: _____

1b. About how long did the discomfort last after the injection? (Check one):

- Less than 1 minute
- 1-2 minutes
- 3-5 minutes
- 6-9 minutes
- at least 10 minutes (Please complete question 1c before leaving the clinic.)

1c. In total, how long did the discomfort last after the injection? (Please enter a number below):

_____ Minutes

Reference:

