10.2.2. Day of Study Drug Administration

The following procedures will be carried out on the day of dosing.

- Symptom-directed PE
- Assessment of vital signs. Note: HR and BP measurements are to be repeated 30 ± 5 minutes, 180 ± 5 , and 360 ± 5 minutes after study drug administration
- Women of childbearing potential will undergo a urine pregnancy test, which must be negative before further participation is allowed
- Prior to dosing, a capillary blood glucose measurement (BGM) will be tested to confirm that blood glucose is in the range of 80 to 150 mg/dL
 - If the blood glucose is > 150 mg/dL after repeat test, then the investigator may treat with a bolus dose of IV regular insulin, per discretion, to bring the subject into the required blood glucose range. Before initiating study treatment, at least 40 minutes should have passed from the last dose of administered insulin and the subject's glucose level should be within the range of 80 to 150 mg/dL.
 - If the blood glucose is < 80 mg/dL after repeat test, then the investigator may treat with oral glucose tabs/solution or IV glucose, per discretion, to bring the subject into the required blood glucose range. Before initiating study treatment, at least 30 minutes should have passed from the last dose of administered glucose and the subject's glucose level should be within the range of 80 to 150 mg/dL.

- If the subject's blood glucose cannot be optimized to 80 to 150 mg/dL within 2 hours, then the visit should be rescheduled after a minimum 24-hour wait, per investigator's discretion.
- Randomization (at Visit 2 only)
- Placement of peripheral catheter and hand placed in heated hand box
- Study drug(s) administration (to be injected over 1 to 3 seconds)
- PK sample collection at 10 ± 2 minutes before and immediately prior to dosing (-2 to 0 minutes), and then 10, 20, 30, 40, 50, 60, 90, 120, 150, 180, 240, 300, and 360 minutes post-dosing (window allowance of ± 2 minutes)
- PD sample collection at 10 ± 2 minutes before and immediately prior to dosing (-2 to 0 minutes), and then 10, 20, 30, 40, 50, 60, 90, 120, 150, 180, 240, 300, and 360 minutes post-dosing (window allowance of ± 2 minutes)
- Injection site assessment at 30, 90, and 360 minutes (± 2 minutes) post-dose using the modified Draize scale ([Appendix 1](#))
- Subject injection site discomfort questionnaire at 10 and 30 minutes (± 2 minutes) post-dose ([Appendix 2](#)). Question Q1c is to be answered at 360 mins post-study drug injection.

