13.9. Local Tolerability

The incidence of any injection site discomfort (score > 0 on the ordinal rating scale) will be analyzed descriptively. The incidences of erythema and edema will be analyzed in a similar manner. Descriptive statistics will be provided for time of onset and duration (of discomfort) and discomfort description (ie, pain, irritation, itching, etc.).

Mean NRS scores will be compared between the treatments.

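### Appendix 2 times Question 1c (total duration of discomfort) at 30 minutes while three other places say 360 minutes; where the appendix is followed, longer durations are right-censored at about 30 minutes

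*Protocol*

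**What the plan says.** Four places in the protocol fix the time of Question 1c, and Appendix 2 does so twice.

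- Appendix 2, staff instructions for the description and duration questionnaire: "All subjects should also answer Question 1c at 30" ± 2 minutes after injection.
- Section 10.2.2: "Question Q1c is to be answered at 360 mins post-study drug injection". Table 2 footnote 11 and Section 11.3.5 give the same 360-minute time.
- Appendix 2, last answer option of item 1b: "at least 10 minutes (Please complete question 1c before leaving the clinic". This reaches only subjects who report discomfort of that length.

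The item itself is "1c. In total, how long did the discomfort last after the injection", answered as a number of minutes. The printed item has no option for discomfort that is still present.

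Section 13.9 states the use of these data: "Descriptive statistics will be provided for time of onset and duration (of discomfort"), together with the description of the discomfort. The same section says that mean NRS scores will be compared between treatments. The synopsis lists the injection site discomfort questionnaires among the secondary safety assessments.

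**The concern.** A question about total duration can be answered only for time that has already passed. Asked at 30 minutes, it closes the record while the subject still has more than five hours of observation left in the clinic. Appendix 2 carries the questionnaire and its staff instructions, so its timing may well be the one followed at the bedside.

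If some staff follow Appendix 2 and others follow the schedule, durations beyond about 30 minutes will be complete in some records and cut off in others, with nothing on the form to show which. What is at stake is the descriptive summary of discomfort duration, part of the local tolerability profile of PRAM9 against the two comparators. The trial randomizes 18 subjects, so even a few cut-off values could shift that summary.

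The related point concerns onset. Section 13.9 plans a summary of time of onset, and the questionnaire does not directly ask for it.

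**Working it through.** The protocol states no figure to reproduce here. The check compares the passages and works out the longest duration that each timing can record.

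**Timing of Question 1c**

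| Place | Time | Who answers |
|---|---|---|
| Appendix 2, staff instructions | 30 ± 2 min | all subjects |
| Appendix 2, item 1b, last option | before leaving the clinic | discomfort of at least 10 min |
| Table 2, footnote 11 | 360 min | not restricted |
| Section 10.2.2 | 360 min | not restricted |
| Section 11.3.5 | 360 min | not restricted |

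Under Section 10.2.2, discharge follows the 360-minute draw and a meal, so the item 1b prompt allows completion after 360 minutes. It therefore disagrees with the staff instruction in the same appendix. Section 6.1 mentions the questionnaire only at 10 and 30 minutes and does not settle the matter.

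**Longest recordable duration.** Discomfort is counted from injection, so the recorded duration cannot exceed the time at which the question is asked.

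- Appendix 2 timing: 30 − 2 = 28 min to 30 + 2 = 32 min.
- Schedule timing: about 360 min.

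For a true duration D and an assessment time T, the recorded value is the smaller of D and T. If D is below 28 minutes, both timings can capture it in full. If D exceeds T, the 30-minute timing records about 30 whatever D is. With no ongoing code, that entry looks the same as a discomfort that really ended at 30 minutes.

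**Other sources for long durations.** Item 1b ("1b. About how long did the discomfort last after the injection") has an open top category starting at 10 minutes. The NRS is taken at 10 and 30 minutes only. Under Section 12.2 an injection site reaction is an adverse event only if it needs medical intervention. None of these recovers an ordinary duration beyond 30 minutes.

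**Time of onset, item by item**

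- NRS: current intensity at 10 and 30 minutes.
- 1a ("1a. How would you describe any discomfort you felt from the study drug"): type of discomfort.
- 1b: duration category.
- 1c: total duration in minutes.

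None of the four asks directly when discomfort began. The NRS gives only a coarse bound: present by 10 minutes, or first present between 10 and 30 minutes.

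**The case against.** The strongest reply is that the form protects the subjects who matter. Anyone whose discomfort outlasts 30 minutes has also passed 10 minutes, and so falls under the item 1b option that points to completion before leaving the clinic. Three other places say 360 minutes. On this view the 30-minute sentence is an isolated error that staff would override.

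This stands in part. The cap is not automatic: it applies only where the 30-minute sentence is followed, and only to discomfort lasting beyond about 30 minutes. But that sentence is an explicit instruction to staff covering every subject, and the protocol does not say which wording prevails.

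A reader might infer more than the documents support:

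- **That 92% of the information is lost.** The ratio (360 − 30)/360 = 91.7% compares two clock times. It would describe only a subject with six hours of discomfort, and the protocol gives no distribution of durations.
- **That the loss is greatest in the worst-tolerated arm.** Truncation affects long durations, but nothing in the protocol says which treatment would have them.
- **That data from different sites cannot be pooled.** Durations that end before 30 minutes can be reported in full at either time. Only the longer ones are affected.
- **That the onset summary would be entirely missing.** The NRS bounds it coarsely. The onset sentence in Section 13.9 also follows one on erythema and edema and may be meant to cover them; the Draize scores at 30, 90 and 360 minutes give a first observed time for those. How onset is derived may also be set out in the statistical analysis plan, which is not shown.

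The endpoint's weight is also modest. Section 13.3.1 names Draize incidence and the NRS under local tolerability, not duration, and Section 13.9 treats duration descriptively.

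**Conclusion.** The contradiction is certain and lies in current text: 30 ± 2 minutes in one instruction, 360 minutes in three places, and a third wording in item 1b.

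Its effect is limited and conditional. Where the Appendix 2 instruction is followed, discomfort lasting beyond about 30 minutes is right-censored at 28 to 32 minutes and cannot be told from a true value of that size. How many records this would touch cannot be estimated, because the protocol gives no expected durations. Shorter durations, the NRS comparison between treatments and the primary glucose endpoint are unaffected.

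The onset point is secondary. No questionnaire item asks directly when discomfort began, so onset of discomfort can be placed only by the two NRS times. This rests on the questionnaire as printed; an additional case report form field, if there is one, could not be checked.

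The point is minor, but the correction is easy and worth making before data collection, because a statistical analysis plan cannot recover a duration that was asked for too early.

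**What to change.** 1. In Appendix 2, change the staff instruction for Question 1c from 30 ± 2 minutes to 360 minutes, matching Table 2 footnote 11, Section 10.2.2 and Section 11.3.5.
2. Make the item 1b prompt and the all-subjects wording agree with that instruction, so that it is clear who answers Question 1c and when.
3. Add a code to Question 1c for discomfort that is still ongoing, so that a censored value can be recognised in the analysis.
4. In Section 13.9, restate time of onset of discomfort as the first observed time point (by 10 minutes, or between 10 and 30 minutes, from the NRS), or delete it.

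The cost is a few wording changes and one extra response code on the form. No visit or blood draw is added, since subjects are already in the clinic until after the 360-minute sample.
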